6.2 Handling of Dropouts or Missing Data (where applicable)

For ITT analysis, patients with partial or missing data to determine morphologic complete remission on the eCRF form will be considered as not having met the criteria morphologic complete remission. For PP analysis and elsewhere, only the complete cases will be analyzed and no missing value imputation will be carried out.

Incomplete AE-related dates will be handled as follows:

- In cases where:
 - o the onset date is completely missing or
 - o the onset is in the same year (only the onset year is available) as the start of study treatment or
 - o the onset is in the same month and year (only the day is missing) as the start of study treatment or
 - o either the onset day or month is missing but the year is not before start of study treatment then the onset date will be replaced by the minimum of start of study treatment and AE resolution date.
- In all other cases the missing onset day or onset month will be replaced by first day or January.

Statistical Analysis Plan

Version: Final

Date of Issue: 20 March 2018

Cantcx Pharmaceuticals, Inc. Protocol No. CNTX-CX-01 2015 AML I Covance Study ID: 000000146201

- Incomplete stopping dates will be replaced by the last day of the month (if the day is missing only), unless this will result in a date after the date of death. If the imputed date will exceed the date of death, the date of death will be used as the stopping date. No imputation is needed if the event is ongoing.
- In all other cases the incomplete stopping date will not be imputed.

To impute missing day of follow-up dates (such as safety long term follow up) or Disease History, the missing day will be taken as the 15th of the month, as long as month and year is available. In all other cases missing or incomplete dates will not be imputed.

In patient listings, the documented date from cCRF will be reported (e.g. .May2016 in case where the day is missing, but month and year are available).

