7.7 Safety

7.7.1 Adverse Events

All adverse events (AEs) recorded on the eCRF will be coded using the MedDRA dictionary [Version 14.1] and classified as either pre-treatment AEs or treatment-emergent AEs (TEAEs) as follows:

- Pre-treatment AEs are events that start prior to the date of first dose of study treatment.
- Treatment-emergent AEs (TEAEs) are events with start date and time on or after the date and time of first dose of study treatment (and up to 30 days after date of last dose of treatment) with

Statistical Analysis Plan

Version: Final

Date of Issue: 20 March 2018

Cantex Pharmaceuticals, Inc. Protocol No. CNTX-CX-01 2015 AML I Covance Study ID: 00000014620 I

start date prior to the date of first dose of study treatment whose severity worsens on or after the date and time of first dose of study treatment.

Assessment of AE severity will be based on the National Cancer Institute-Common Terminology Criteria for Adverse Events (NCI-CTCAE, version 4.0.3).

All AE data will be listed by treatment group including Pre-treatment AEs and TEAEs. The number and percentage of subjects reporting each treatment AE and TEAEs will be summarized for each treatment group and overall, by System Organ Class (SOC) (sorted alphabetically) and Preferred Term (**PT**) (sorted by descending overall total) for Safety populations.

In addition, corresponding listings of serious AEs (SAEs), AEs leading to discontinuation of treatment, AEs causing interruptions from study treatment, AEs causing dose reduction from study treatment and study treatment-related AEs causing dose reductions are provided.

An overview table will summarize the number and percentage of subjects with at least one of the following AEs/TEAEs, where subjects with more than one AEs/TEAE in a particular category are counted only once in that category:

- any AE;
- any TEAEs;
- treatment-related TEAE;
- any AE by maximum NCI-CTCAE grade; treatment-related TEAE by maximum NCI-CTCAE grade;
- AE leading to treatment interruption;
- treatment-emergent AEs leading to treatment interruption;
- AE leading to treatment reduction;
- treatment-emergent AEs leading to treatment reduction;
- AE leading to treatment discontinuation; treatment-emergent AEs leading to discontinuation from the study;
- SAE;
- treatment-emergent SAE;
- SAE leading to death;
- treatment-emergent SAE leading to death;
- SAE leading to treatment discontinuation;

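### The fourth AE onset-date condition in SAP 6.2 overrides a recorded month, so an unresolved screening event known to precede treatment can be counted as a TEAE

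*SAP*

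**What the plan says.** SAP 6.2 lists four situations in which an incomplete AE onset date is sent to one rule: "the onset date will be replaced by the minimum of start of study treatment and AE resolution date". The situations are:

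1. The onset date is completely missing.
2. Only the year is known, and it is the year of first dose.
3. "the onset is in the same month and year (only the day is missing) as the start of study treatment or"
4. "either the onset day or month is missing but the year is not before start of study treatment"

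A fallback follows: "In all other cases the missing onset day or onset month will be replaced by first day or January".

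SAP 7.7.1 then classifies events by start date. "Pre-treatment AEs are events that start prior to the date of first dose of study treatment". TEAEs are "events with start date and time on or after the date and time of first dose of study treatment", with the window running "and up to 30 days after date of last dose of treatment". Events that began before first dose and worsen afterwards also count as TEAEs.

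Pre-dose events exist by design. Protocol 6.6.3.1 collects AEs from informed consent, and Protocol 6.5.2 allows up to 28 days of screening.

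**The concern.** The third condition limits the missing-day case to the calendar month of first dose, where the order of onset and dosing really is unknown. The fourth removes that limit. It looks only at the year, so it catches every missing-day record in the treatment year or later and ignores a month that is on file. The first-of-month fallback is left for years before the treatment year only.

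This goes further than conservative imputation, which fills in what is unknown. Here a recorded fact is replaced by a date that contradicts it. TEAE summaries are the key safety endpoints (SAP 3.3), and safety is one of the two primary objectives (SAP 2.2). Events known to have begun before treatment add noise to those summaries and carry no information about CX-01.

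**Working it through.** The plan states no figure on this point, so there is nothing to reproduce. The check applies the written rule to cases, then counts how often it matters.

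**Cases.** First dose is set at 10 March 2017 for illustration. In every case the onset day is missing and the month is known.

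| Recorded onset | Resolution | SAP 6.2 as written | Without the fourth condition |
|---|---|---|---|
| Feb 2017 | ongoing, or 20 Mar | 10 Mar 2017, TEAE | 1 Feb 2017, pre-treatment |
| Feb 2017 | 1 Mar | 1 Mar 2017, pre-treatment | 1 Feb 2017, pre-treatment |
| Mar 2017 | ongoing | 10 Mar 2017, TEAE | 10 Mar 2017, TEAE |
| May 2017 | 20 May | 10 Mar 2017, TEAE | 1 May 2017, TEAE* |
| Jan 2018 | ongoing | 10 Mar 2017, TEAE | 1 Jan 2018, TEAE* |
| Dec 2016 | ongoing | 1 Dec 2016, pre-treatment | 1 Dec 2016, pre-treatment |

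*If within 30 days of last dose; beyond that window, the written rule still gives a TEAE, wrongly.

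The first row is the status error. Set against the last row, it also shows an inconsistency: an onset in the month before first dose is handled correctly if New Year falls between the two dates, and wrongly otherwise.

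**How often a screening onset is caught.** Assumptions: first dose equally likely on each of the 365 days of 2017; onset equally likely on each of the 28 days before it; onset day missing; event unresolved at first dose.

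- Combinations: 365 × 28 = 10,220.
- With first dose on day *d* of a month, 29 − *d* of the 28 days fall in the previous month (none if *d* > 28). The sum over *d* = 1 to 28 is 28 × 29 / 2 = 406 per month, or 12 × 406 = 4,872 per year.
- Share with onset in a different month: 4,872 / 10,220 = 47.7%.
- January first doses (406) cross the year boundary and go to the fallback. The other 11 × 406 = 4,466 become TEAEs: 4,466 / 4,872 = 91.7%.
- Labelled TEAE under the written rule: (10,220 − 406) / 10,220 = 96.0%.
- Labelled TEAE without the fourth condition: (10,220 − 4,872) / 10,220 = 52.3%. These are the same-month records, where the order is unknown and counting them is a defensible choice.

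**Date error for later onsets.** For a true onset on Day *k* with resolution after first dose, the written rule is wrong by *k* − 1 days. Over Days 61–120 the mean is (60 + 119) / 2 = 89.5 days and the maximum 119. Using the first of the known month, the mean is (7 × 465 + 4 × 435 + 378) / 365 = 14.7 days and the maximum 30. The terms are the sums of 0 to *L* − 1 for months of length *L* = 31, 30 and 28.

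**The case against.** The case against making much of this is substantial, and most of it stands.

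A reader might infer that every partly dated onset is moved to the first-dose day. It is not. The rule takes the earlier of first dose and resolution, so an event known to have resolved before dosing stays pre-treatment.

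A reader might infer that late events are widely misclassified. An onset after first dose and within 30 days of last dose is a TEAE on either date. A status error needs a record outside that window. Protocol 6.6.3.1 normally stops collection there, with an extension mainly for patients without ANC recovery by Day 42.

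A reader might infer that consolidation events would contaminate the induction safety results. No AE table in SAP 7.7.1 or the table list is by cycle, and SAP 6.2 has listings print the recorded date. Duration appears only in the AE listing shell, as far as its damaged text can be read.

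The affected group is narrow. Pre-dose events that worsen after dosing are TEAEs anyway. One paragraph of Protocol 6.6.3.2.1 counts conditions present before study drug as AEs only if they worsen, although another paragraph of the same section is broader. Protocol 6.7 and 8.2 plan edit checks and data queries, which should reduce partial dates.

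The rule is the same in all arms and screening precedes randomization, so no bias between arms is shown.

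None of this answers the narrow point. The fourth condition as written overrides a known month and makes the third redundant.

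**Conclusion.** The defect is real and small. A screening event with a recorded earlier month in the treatment year, unresolved at first dose, is turned into a TEAE against SAP 7.7.1, unless it worsens after dosing and so qualifies anyway. An onset known to lie beyond the 30-day window would also be labelled a TEAE, rarely. For other later onsets only the derived day and duration suffer.

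The percentages above describe how the rule behaves for a record of the given type, under evenly spread dates. They do not say how many such records exist. One could assume 10 AEs in each of 75 patients and 1–3% partial dates, giving 750 × 0.01 = 7.5 to 750 × 0.03 = 22.5 records. Neither input is in the documents. The product also counts all partial dates, including same-month ones that no correction would move, so it is not a count of misclassified events. That number is unknown and probably small.

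**What to change.** Delete the fourth condition in SAP 6.2. The rule then reads:

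- **Earlier of first dose and AE resolution:** onset completely missing; only the year known and equal to the treatment year; or month and year known and equal to those of first dose.
- **First day of the recorded month:** month and year known and different from those of first dose, whether earlier or later.
- **1 January of the recorded year:** only the year known, and later than the treatment year.

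The existing fallback already delivers the last two once the fourth condition is gone.

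Keep the resolution date in the first item. Without it, an onset in March (day unknown) that resolved on 5 March, with first dose on 10 March, would be given an onset after its own resolution and become a TEAE. Keep the rule for a completely missing onset as well, since nothing else covers it.

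It would help to add one sentence saying whether the study-day and duration columns of the AE listing use the recorded or the imputed date.

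The cost is one wording change and one date derivation in the programs. No new data are needed.

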6.5.7 Long Term Follow-Up

After Safety Follow-Up Visit, the relapse and survival data will be collected every 3 months.

Each subject will participate in the long term follow-up for approximately 18 months from the time of informed consent until death or until the end of the study (for the definition of end of study, see Section 6.1).

Investigational sites are expected to make every effort to obtain long term follow-up data. This level of diligence is necessary to ascertain the patient's health status, and thus avoid lost to follow-up status for efficacy assessments. Follow-up may require:

- Permission for study personnel to contact an alternative person (e.g., family, spouse, partner, legal representative, or physician) even if only by telephone
- Permission for study personnel to access and review the patient's medical information from alternative resources (e.g., doctors notes, hospital records)

Attempts to contact patients must be documented in the patient's source documents and in the eCRF. The source documents for OS may be sent remotely to the site Clinical Research Associate for review and verification (ensuring patient identifiers are redacted except for study number and initials).

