7.2 Subject Disposition and Data Sets Analyzed

Subject disposition will be listed and summarized by treatment group and overall and will include the number and percentage of subjects:

- screened;
- randomized;
- randomized and not treated;
- treated;
- available at each study visit (treatment period, 30 day safety follow-up, long term follow-up at every 3 months until approximately 18 months or deaths of all patients, whichever is earlier);
- included in each study population (ITT, PP, Safety).

In addition, the number and percentage of subjects who complete the study and who discontinued early, including a breakdown of the primary reasons as reported in the eCRF for early termination, will be presented for all analysis populations (ITT, PP, Safety). Additional summaries for safety follow up (reasons for not completing safety follow up) and long term follow up (status of long term follow up, cause of death recorded at long term follow up) will be provided for each treatment arm for the ITT, PP and safety population.

A summary of patient enrollment by site will also be provided by treatment group and overall for the ITT population.

A summary of the reasons for screen failure as well as the number of subjects screened but not randomized will be produced. No other information for screen failures will be presented.

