7.4 Demographics and Other Baseline Characteristics

Demographic and baseline characteristics will be listed and summarized by treatment group and overall for all analysis populations (ITT, PP, Safety). Standard descriptive statistics will be presented for the continuous variables of:

- Age at screening (years) [calculated as (informed consent date - date of birth)/365.25 and reported as whole years];
- weight (kg);
- height (cm);
- BMI
- Time since diagnosis
- Baseline blasts in bone marrow(%)
- Baseline LDH

The total counts and percentages of subjects will be presented for the categorical variables of:

- age group (years) (grouped as <70 and 2: 70);
- sex;
- race;
- ethnicity;
- AML type (de novo or secondary);
- Baseline peripheral blasts (Yes/No)
- ECOG performance status
- Time since diagnosis(<= 30 days,> 30 days)

No formal tests of statistical significance will be performed on the demographic and baseline data.

Other baseline measurements, such as bone marrow aspirate/biopsy, pregnancy test result, lab parameters, vital signs, ECG and ECOG, will be summarized by treatment group with the post-baseline measurements.

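### SAP 6.2 sets a missing day to the 15th without bounds: a partial diagnosis date can fall after randomization and, if relapse and death dates are covered, an event can precede remission or last contact

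*SAP*

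**What the plan says.** SAP 6.2 introduces the rule with "To impute missing day of follow-up dates (such as safety long term follow up) or Disease History" and then states that "the missing day will be taken as the 15th of the month, as long as month and year is available". No minimum or maximum is attached, and none is given in SAP 6.1, in the endpoint definitions of SAP 3.2 or in the list of changes in SAP 8. Everything else falls under "In all other cases missing or incomplete dates will not be imputed".

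Adverse-event dates in the same section are bounded. For a stop date, "If the imputed date will exceed the date of death, the date of death will be used as the stopping date". For an onset date, in the listed cases, "the onset date will be replaced by the minimum of start of study treatment and AE resolution date".

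The dates concerned are used as follows:

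- **Diagnosis.** SAP 7.4 summarizes time since diagnosis as a continuous variable and as a split, "Time since diagnosis(<= 30 days,> 30 days".
- **Relapse and survival.** Protocol 6.5.7: "After Safety Follow-Up Visit, the relapse and survival data will be collected every 3 months". SAP 7.2 summarizes long-term follow-up status and "cause of death recorded at long term follow up". SAP 3.2 builds EFS, LFS, OS and duration of CR from relapse and death dates.

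The rule does not name death or relapse dates.

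**The concern.** The rule ignores dates already known for the same patient. The SAP guards adverse-event dates against impossible orderings but leaves the dates behind time since diagnosis, and possibly those behind survival and remission duration, without a guard. Patients are newly diagnosed, so diagnosis and randomization may be only days apart, less than the error the rule can introduce. A negative interval would then have to be dealt with by an unplanned programming decision, in an open-label trial, after the data have been seen.

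The scope is also unclear. If a partial death date is a follow-up date, it goes to the 15th without a bound. If it is not, it stays unimputed and the SAP has no rule for that patient's OS time.

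**Working it through.** The documents give no figure to reproduce, so the check applies the rule to every day of a 365-day year.

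**Inputs.** The 15th-of-month rule is from SAP 6.2. Two things are assumed: dates are spread evenly over the year, and the true gap *g* in days takes the values shown. The documents give neither the gaps nor the number of day-missing dates. Time since diagnosis is taken to run to randomization.

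**Size of the error.** Imputed minus true day runs from 15 − 31 = −16 to 15 − 1 = +14 days; the mean absolute error over the year is 7.6 days.

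**Diagnosis after randomization.** Let *r* be the day of the month of randomization. The imputed date is later than randomization only if both fall in the same month (*r* ≥ *g* + 1) and *r* ≤ 14. That leaves 14 − *g* days per month, so

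share = 12 × (14 − *g*) / 365

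- *g* = 3: 12 × 11 / 365 = 132/365 = 36%
- *g* = 10: 12 × 4 / 365 = 48/365 = 13%
- *g* = 14 or more: 0%
- averaged over gaps of 0-7 days 35%, 0-14 days 23%, 0-28 days 12%

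Time since diagnosis can reach −14 days. Example: randomization on 9 June and diagnosis recorded only as June gives 15 June, so 9 − 15 = −6 days.

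**Event before an earlier known date.** This applies if relapse and death dates are covered. Let *a* be the day of the month of the known date (last contact, or CR). The imputed event precedes it only if both fall in the same month and *a* ≥ 16. In a month of *L* days that leaves *L* − 15 − *g* days. Summed over the year (valid for *g* up to 13),

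share = (365 − 12 × 15 − 12*g*) / 365 = (185 − 12*g*) / 365

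- *g* = 3: 149/365 = 41%
- *g* = 7: 101/365 = 28%
- averaged over 0-91 days: each month contributes *m*(*m* + 1)/2 with *m* = *L* − 15. The year's total is 7 × 136 + 4 × 120 + 91 = 1,523, and 1,523 / (365 × 92) = 4.5%
- the largest gap affected is 31 − 16 = 15 days, so the share is 0% at 31 days or more

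The interval can reach −16 days. Example: last contact on 20 May and death recorded as May gives 15 May, which is 5 days before that contact.

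**Death before randomization.** With randomization as the known date, the same condition requires a death within 15 days, in the same calendar month, with randomization on day 16 or later and the day of death missing.

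**With bounds.** Taking diagnosis as the earlier of the 15th and randomization, and death as the later of the 15th, randomization and last date known alive, impossible orderings fall to 0% in every scenario run.

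**The case against.** The strongest reply is about scope and size:

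- Death dates are not named in the rule. Early deaths would come in through adverse-event and SAE reporting (Protocol 6.6.3.2.1 and 6.6.4), and SAP 6.2 itself uses the date of death as a known anchor.
- Long-term contacts are every 3 months, so a gap of 3-7 days between last contact and death is not what the schedule implies.
- Whenever diagnosis is placed after randomization, the true gap is at most 13 days. The patient stays in the 30-days-or-less category, and only the continuous summary shifts. SAP 7.4 plans no tests on baseline data.
- SAP 7.6.2 calls the EFS, LFS and OS analyses descriptive.
- Protocol 6.7 and 8.2 provide validation programs, entry checks and queries to sites.

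Most of this stands as a limit on size. It does not remove the point. Data checks may flag a bad ordering, but they do not change the imputation rule. If death dates fall outside the rule, OS has no rule for a partial death date.

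A reader might infer that the rule makes negative OS a general risk. The documents do not support that. Long-term follow-up starts after a safety visit about 30 days after the last cycle (Protocol 6.5.5 and 6.5.7), whereas this error needs a death within 15 days of randomization. A reader might also infer that a death dated before randomization shifts Day 30 mortality by 1/25, or 4 points of an arm. It would still count as a death by Day 30, so the rate would not move.

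**Conclusion.** The point holds as a minor defect of a stated rule. The diagnosis limb is firmest, because disease history is named and the population is newly diagnosed. The relapse and death limb is conditional on those dates being covered, which the SAP should say. Death before randomization is possible only for a narrow set of early deaths.

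The percentages apply per day-missing date and rest on evenly spread calendar dates and assumed gaps. For death before last contact, the 41% and 28% figures belong to gaps of 3 and 7 days; for contacts spread over a 3-month interval, 4.5% is the closer guide. The total effect cannot be sized, because the number of partial dates is unknown. The primary CR test and the sample size do not depend on this rule.

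**What to change.** Add to SAP 6.2:

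- The 15th-of-month rule also applies to partial relapse and death dates.
- An imputed diagnosis date is the earlier of the 15th and the randomization date.
- An imputed death date is the latest of the 15th, the randomization date and the last date the patient was known alive.
- An imputed relapse date is not earlier than the CR (or leukemia-free state) date or the last assessment documenting remission, and not later than the date of death.

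Randomization is a safer cap for diagnosis than informed consent. Protocol 6.5.2 places the screening marrow after consent, and a consent cap would force a wrong date if that marrow established the diagnosis.

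The cost is a few lines in the SAP and one programming condition, using dates the study already collects.
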